# 9.4.3 Handling and disposal

As with other potentially toxic anticancer agents, care should be exercised in the handling and preparation of infusion solutions prepared from ELOXATIN. The use of gloves is recommended. If a solution of ELOXATIN contacts the skin, wash the skin immediately and thoroughly with soap and water. If ELOXATIN contacts the mucous membranes, flush thoroughly with water. Procedures for the handling and disposal of anticancer drugs should be considered.

#### 9.4.4 Adverse Events

For a comprehensive list of adverse events please refer to the package insert for Oxaliplatin/Eloxatin

- Central nervous system: Peripheral neuropathy, fatigue, pain, headache, insomnia, rigors, dizziness.
- Cardiovascular: Edema, chest pain, peripheral edema, flushing, thromboembolism.
- Gastrointestinal: Nausea, diarrhea, vomiting, abdominal pain, constipation, anorexia, stomatitis, dyspepsia, dysgeusia, flatulence, hiccups, mucositis, gastroesophageal reflux disease, dysphagia.
- Hematologic & oncologic: Anemia, thrombocytopenia, leukopenia, neutropenia.
- Hepatic: Increased serum AST, increased serum ALT, increased serum bilirubin.
- Endocrine & metabolic: Dehydration, hypokalemia.
- Neuromuscular & skeletal: Back pain, arthralgia.
- Respiratory: Dyspnea, cough, upper respiratory tract infection, rhinitis, epistaxis, pharyngitis, pharyngolaryngeal dysesthesia.
- Renal: Increased serum creatinine
- Dermatologic: Skin rash, alopecia, palmar-plantar erythrodysesthesia
- Hypersensitivity: Hypersensitivity reaction (includes urticaria, pruritus, facial flushing, shortness of breath, bronchospasm, diaphoresis, hypotension, syncope)
- Local: Injection site reaction

Version Date: 13AUG2018 Confidential Page 37 of 51

• Ocular: Abnormal lacrimation

• Miscellaneous: Fever

#### 10 ADVERSE EVENTS

The descriptions and grading scales found in the revised NCI Common Terminology Criteria for Adverse Events (CTCAE) v4 will be utilized for AE reporting. A copy of the CTCAE v4 can be downloaded from the CTEP website at http://ctep.cancer.gov

#### 10.1 Definitions

#### **10.1.1** Adverse Event

An Adverse Event (AE) is any untoward medical occurrence whether or not considered related to the study drug that appears to change in intensity during the course of the study. The following are examples of AEs:

- Unintended or unfavorable sign or symptom
- A disease temporally associated with participation in the protocol
- An intercurrent illness or injury that impairs the well-being of the subject

Abnormal laboratory values or diagnostic test results constitute AEs only if they induce clinical signs or symptoms or require treatment or further diagnostic tests

Hospitalization for elective surgery or routine clinical procedures that are not the result of an AE (e.g., surgical insertion of central line) should not be recorded as an AE.

Disease progression should not be recorded as an AE, unless it is attributable to the study regimen by the site investigator.

## **10.1.2** Serious Adverse Event

A serious adverse event (SAE) is any untoward medical occurrence resulting in one or more of the following:

- Death- Death due to progression is not considered a SAE unless the site investigator feels the study drug contributed to disease progression.
- Is life-threatening (defined as an event in which the subject was at risk of death at the time of the event; it does not refer to an event which hypothetically might have caused death if it were more severe)
- Requires inpatient hospitalization or prolongation of existing hospitalization
- Results in persistent or significant disability/incapacity
- Is a congenital anomaly or birth defect
- Is an important medical event (defined as a medical event(s) that may not be immediately life-threatening or result in death or hospitalization but, based upon appropriate medical and scientific judgment, may jeopardize the subject or may require intervention (e.g., medical, surgical) to prevent one of the other serious outcomes listed in the definition above). Examples of such events include, but are not limited to, intensive treatment in an emergency room or at home for allergic

Version Date: 13AUG2018 Confidential Page 38 of 51

bronchospasm; blood dyscrasias or convulsions not resulting in hospitalization; or the development of drug dependency or drug abuse.

# **10.1.3** Unexpected Adverse Event

For this study, an AE is considered unexpected when it varies in nature, intensity or frequency from information provided in the current IB, prescribing information or when it is not included in the informed consent document as a potential risk. Unexpected also refers to AEs that are mentioned in the IB as occurring with a class of drugs or are anticipated from the pharmacological properties of the drug, but are not specifically mentioned as occurring with the particular drug under investigation.

## 10.1.4 Relatedness

AEs will be categorized according to the likelihood that they are related to the study drug(s). Specifically, they will be categorized using the following terms:

Unrelated	Adverse Event is not related to the study drug(s)
Unlikely	Adverse Event is doubtfully related to the study drug(s)
Possible	Adverse Event may be related to the study drug(s)
Probable	Adverse Event is likely related to the study drug(s)
Definite	Adverse Event is clearly related to the study drug(s)

# 10.2 Reporting adverse events

## 10.2.1 Adverse Event (AE)

- AEs will be recorded from time of signed informed consent until 30 days after discontinuation of study drug(s).
- AEs will be recorded regardless of whether or not they are considered related to the study drug(s).
- All AEs will be recorded in the subject's medical record and on the appropriate study specific eCRF form within EDC system.
- AEs considered related to study drug(s) will be followed until resolution to Grade ≤ 1 or baseline, deemed clinically insignificant, and/or until a new anti-cancer treatment starts, whichever occurs first.

## 10.2.2 Serious Adverse Event (SAE)

# 10.2.2.1 Site Requirements for Reporting SAEs to HCRN

- SAEs will be reported from time of signed informed consent until 30 days after discontinuation of study drug(s).
- SAEs will be reported on the SAE Submission Form **within 24 hours** of discovery of the event
- SAEs include events related and unrelated to the study drug(s).
- All SAEs will be recorded in the subject's medical record and on the appropriate study specific eCRF form within EDC system.

Version Date: 13AUG2018 Confidential Page 39 of 51

• All SAEs regardless of relation to study drug will be followed until resolution to ≤ Grade 1 or baseline and/or deemed clinically insignificant and/or until a new anticancer treatment starts, whichever occurs first.

The completed SAE Submission Form must be sent electronically to [contact]. The site investigator is responsible for informing the IRB and/or the Regulatory Authority of the SAE as per local requirements. The original copy of the SAE Submission Form and the email correspondence must be kept within the Trial Master File at the study site.

Once the SAE has resolved (see resolution guidelines listed in 11.2.2.1), sites must submit a follow-up SAE Submission Form within a reasonable timeframe to HCRN electronically to [contact].

# 10.2.2.2 HCRN Requirements for Reporting SAEs to Eli Lilly

HCRN will report all SAEs to Eli Lilly at Global Patient Safety via fax **within 24 hours** of receipt of the SAE Submission Form from the site. The fax number to send the form is [contact] or [contact]. Follow-up information will be provided to Eli Lilly and Co. as reasonably requested.

## 10.2.2.3 Sponsor-Investigator Responsibilities

HCRN will send a SAE summary to the sponsor-investigator **within 24 hours** of receipt of SAE Submission Form from a site. The sponsor-investigator will promptly review the SAE summary and assess for expectedness and relatedness.

# 10.2.2.4 HCRN Requirements for Reporting to the Food and Drug Administration (FDA)

This protocol was determined to be exempt from the requirements of an IND by the FDA. HCRN will continue to facilitate compliance of applicable requirements for the sponsor-investigator in relation to this study. This includes but is not limited to 21 CFR 50.20 informed consent, 21 CFR Part 56 IRB, and pertinent sections of the Public Health Service Act and FDAAA.

#### 11. STATISTICAL METHODS

## 11.1 Study Design

This is a phase II, multicenter, double-blinded, randomized, 2-arm trial evaluating the efficacy and safety of mFOLFIRINOX + RAM (Arm A) vs. mFOLFIRINOX + placebo (Arm B) in 85 subjects with advanced PCA, not amenable to curative treatment. Subjects will be randomized in a 1:1 ratio (i.e., there will be 43 subjects in the control group and 42 subjects in the treatment group). The primary objective of this trial is to estimate and compare PFS in Arm A versus Arm B. See section 11.10 for a description of the power/sample size analysis based on the logrank test.

Version Date: 13AUG2018 Confidential Page 40 of 51

# 11.2 Definition of Primary Endpoint

PFS is based upon the time of enrollment until progression or death. Disease is evaluated by CT/MRI scans of the organ(s) with the target lesion(s) based on RECIST 1.1 criteria.

# 11.3 Definitions of Secondary Endpoints

Overall survival is defined as the time of enrollment to time of death. Response is defined as a complete or partial response according to CT/MRI evaluations based on RECIST 1.1 criteria. CTCAE v4 is used to grade toxicities.

# 11.4 Analysis Plan for Primary Objective

PFS will be estimated for each arm using the method of Kaplan and Meier. Nine month PFS will be reported along with a 95% confidence interval. PFS will be compared between Arm A and Arm B using a one-sided logrank test. The ITT analysis dataset will be used for this analysis.

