# 2.2 Endpoints

# 2.2.1 Primary Endpoint

Nine month PFS is based upon the time of registration until progression or death. Disease is evaluated by CT/MRI scans of the organ(s) with the target lesion(s) based on RECIST 1.1 criteria.

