#### 4. SUBJECT REGISTRATION

All subjects must be registered through HCRN electronic data capture (EDC) system. A subject is considered registered when an "On Study" date is entered into the EDC system.

Subjects must be registered and randomized prior to starting protocol therapy. Subjects must be randomized within one business day of registration and begin therapy within 5 business days of randomization.

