- 8: Scans to be repeated every 8 weeks (± 7 days) until progression of disease. Pre-treatment scans to be performed within 28 days prior to registration.
- 9: For subjects who discontinue study treatment without radiographically documented PD, the investigative sites will continue to evaluate tumor response every 8 weeks ( $\pm$  7 days) by the same method used at baseline and throughout the study until time of disease progression, death or until study completion, except when not feasible in the opinion of the site investigator due to subject's clinical status. After the subject has documented PD, radiologic assessments are no longer required and the subject will be followed every 8 weeks ( $\pm$  7 days) until the subject's death or study completion, whichever is earlier.
- 10: If the TSH is abnormal, a total T3 and free T4 should be ordered.
- 11: Coagulation tests should be periodically repeated during the course of the study per site investigator discretion.

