# 7.1.2 On Treatment; Day 1 of each cycle

*Note:* Day 1 lab testing need not be repeated if completed within 7 days of starting protocol therapy.

- Physical examination
- Vitals Signs (including blood pressure), Weight [kg] and ECOG PS
- Laboratory Testing:
  - CBC with differential: Hemoglobin, hematocrit, erythrocyte count (RBC), mean cell volume, mean cell hemoglobin concentration, leukocytes (WBC), neutrophils, lymphocytes, monocytes, basophils, platelets.
  - o CMP: Sodium, potassium, total bilirubin, alkaline phosphatase, alanine aminotransferase (ALT), aspartate aminotransferase (AST), blood urea nitrogen (BUN), creatinine, calcium, random glucose, albumin
  - Magnesium and uric acid
  - o CA 19-9 every 2 cycles
  - o Urinalysis including a urine dipstick for protein if quantification needed
- CT or MRI of chest, abdomen/pelvis after every 2 cycles of treatment
- mFOLFIRINOX and ramucirumab/placebo

Version Date: 13AUG2018 Confidential Page 27 of 51

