# **8.3.7 Progression Free Survival**

A measurement from the date of randomization until the criteria for disease progression is met as defined by RECIST 1.1 or death occurs. Subjects who have not progressed will be right-censored at the date of the last disease evaluation.

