## 11.10 Sample Size/Accrual/Study Duration

We aim to test the null hypothesis of PFS at 6 months. Using a one-sided log-rank test we have estimated a sample size of 85 patients (43 in one and 42 in another arm) which will provide 80% power under a type 1 error of 20%. This is an estimation on 24 months accrual and 9 months follow up after accrual for the primary endpoint. Sample size may increase to 95 to account for a 10% drop out rate.

The expected progression free survival for mFOLFIRINOX in metastatic pancreatic cancer is 6 months. The addition of RAM to mFOLFIRINOX would be expected to increase the median PFS to at least 9 months. We assume a type 1 error ( $\alpha$ ) of 0.2 and a power (1- $\beta$ ) of 80%.

With an exact power of 0.8014, hazard ratio of 0.6667 and endpoint of detecting 3 months PFS advantage of the mFOLFIRINOX/ramucirumab combination over mFOLFIRINOX alone (from 6 to 9 months), the sample size on each arm was calculated to be 43 in the control arm and 42 in the treatment arm (total is 85). 29.30

The estimated enrollment period for this study is 24 months and the estimated study duration is 33 months.

Version Date: 13AUG2018 Confidential Page 43 of 51

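### Nine-month PFS is read about six days before the nominal week-40 scan, so each arm's figure mostly reflects progression found by week 32 and probably runs a few points high

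*Combined protocol and SAP*

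**What the plan says.** Section 11.4 (Analysis Plan for Primary Objective) estimates PFS per arm by Kaplan-Meier, compares the arms with a one-sided log-rank test, and singles out one PFS summary: "Nine month PFS will be reported along with a 95% confidence interval". Section 2.2.1 gives the same landmark as the primary endpoint: "Nine month PFS is based upon the time of registration until progression or death". Section 8.3.7 defines PFS as "A measurement from the date of randomization until the criteria for disease progression is met as defined by RECIST 1.1 or death occurs", and censors subjects without progression at their last disease evaluation.

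The scan schedule is worded in two ways. Footnote 8 of the Section 7 study calendar reads "Scans to be repeated every 8 weeks (± 7 days) until progression of disease". Section 7.1.2 reads "CT or MRI of chest, abdomen/pelvis after every 2 cycles of treatment", where a cycle is 28 days and, under Section 5.3.1, a missed dose delays the cycle. The documents give no anchor date for the 8-week schedule and no month-to-day conversion. They have no rule for setting nine-month status from the week-40 scan and name no interval-censored method.

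On timing, Section 4 says "Subjects must be randomized within one business day of registration and begin therapy within 5 business days of randomization". Section 11.10 says "This is an estimation on 24 months accrual and 9 months follow up after accrual for the primary endpoint".

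**The concern.** Radiographic progression can be dated only when someone looks. A landmark placed just before a scheduled scan therefore counts as progression-free almost everyone who progressed since the previous scan. Here the gap is nearly a full 8-week interval, and it goes the same way in both arms.

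What is at stake is the per-arm number. A reader will take it as the proportion free of progression at nine months, although most of its scan information stops at about 7.4 months. It could then be carried into a go/no-go decision or set beside figures from trials with other scan schedules. The randomized comparison is a separate matter, since both arms share the same schedule.

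**Working it through.** **The plan's own figure first.** Section 11.10 gives medians of 6 and 9 months (hazard ratio 0.6667), one-sided alpha 0.20, 24 months' accrual, 9 months' follow-up, 43 + 42 subjects and power 0.8014. With exponential PFS and uniform accrual, P(event) = 1 − e^(−9λ)(1 − e^(−24λ))/(24λ), λ = ln 2/median. This is 0.880 (control) and 0.772 (treatment), or 70.3 expected events among 85. Schoenfeld power is Φ(√70.3 × 0.4055/2 − 0.8416) = 0.805; a Lakatos-type integration gives 0.803. The stated power reproduces, so the same model is used below.

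**Dates.**
- Nine months: 9 × 30.4375 = 273.9 days.
- Week 32: day 224 = 7.36 months.
- Week 40: day 280 = 9.20 months, window days 273 to 287.
- Share of week-40 scans done by the landmark, if timing is uniform in the window: (273.9 − 273)/14 = 6.7%. If scans run from a first dose 0 to 9 days after registration, it is about 0.3%.
- Randomization comes within one business day of registration, so that choice of time zero is negligible here.

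**Excess if all progression is scan-detected and the medians are true progression times.** S(t) = 2^(−t/median):

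| | S(day 224) | S(day 273.9) | Excess |
|---|---|---|---|
| Control, median 6 | 0.427 | 0.354 | 7.4 points |
| Treatment, median 9 | 0.567 | 0.500 | 6.7 points |

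The between-arm difference goes from 0.146 to 0.140, a change of about 0.7 points before rounding.

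**Deaths, dated when they occur.** The documents give no share of PFS events that are deaths without prior progression, so 0 to 30% is an assumed range. Simulation with the ± 7 day window and scans timed from first dose gives:

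| Death share | Control | Treatment |
|---|---|---|
| 0% | +6.6 | +6.1 |
| 15% | +5.6 | +5.1 |
| 30% | +4.6 | +4.2 |

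With scans timed from registration, the no-death figures are +6.9 and +6.3. Against the true nine-month value, coverage of the nominal 95% interval in simulated trials of 43 and 42 was 0.87 to 0.92.

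**If scans follow delayed cycles.** A week-32 scan 14 days late falls on day 238, and the excess is 5.2 (control) and 4.8 (treatment). At 28 days late (day 252) it is 3.1 and 2.9. With 30% deaths, multiply by 0.7: 3.6 and 3.3, then 2.1 and 2.0. The range is about 2 to 5 points.

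**If the medians are already scan-detected.** Detection lags progression by about 28 days on average, half an interval. The value just before the week-40 scan is then S(224 + 28), that is 0.384 and 0.529, against the smooth curve's 0.354 and 0.500. The excess is 3.1 and 2.9 points, and less once deaths are allowed for.

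**Follow-up.** A cut-off 9 months after the last enrolment (day 274) falls 20 days short of day 294. With even accrual over 730 days, 20/730 × 85 ≈ 2 subjects are affected.

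**Does a later reading work?** On a fixed calendar from first dose, reading the curve at day 294 gives estimates of about 0.34 and 0.48 to 0.49. True week-40 PFS is 0.346 and 0.492, and coverage is 0.93 to 0.95. If scans instead drift 14 to 28 days by the fifth scan, the day-294 reading is itself about 2 to 5 points above true week-40 PFS. The change therefore depends on settling the scan schedule first.

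**The case against.** The strongest reply concerns the estimand. Section 8.3.7 ends PFS when RECIST criteria are met, which happens at an assessment. For documented-progression PFS, Kaplan-Meier at nine months estimates what is defined, and any landmark between scans shares this feature. Nor does Section 11.10 say that its medians are true progression times; it says only "The expected progression free survival for mFOLFIRINOX in metastatic pancreatic cancer is 6 months". This stands in part. It lowers the size to about 3 points on that reading and lowers the seriousness. It does not make the nine-month label informative when nearly all scan information stops at week 32.

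Three stronger readings are tempting, and the documents do not support them.
- That the figure simply is week-32 PFS and is 5 to 7 points too high. Deaths and off-schedule scans, including the end-of-treatment scan, count on their own dates. Day 274 also lies just inside the week-40 window. The 5-to-7 range needs few deaths, true-progression medians and fixed calendar scans.
- That the treatment comparison is biased. It rests on a log-rank test over all PFS times, with one schedule for both arms.
- That the 9-month follow-up is seriously short. About two subjects are affected, and Section 7.1.6 keeps off-treatment scans going until progression, death or study completion.

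It is also fair to say that the interval half-width is about 14 to 15 points per arm (1.96 × √(p(1 − p)/42)), and that the plan specifies no comparison with outside nine-month figures.

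**Conclusion.** The point holds for the per-arm nine-month estimate, and only there. On the calendar schedule the landmark precedes the nominal week-40 scan by about 6 days, and nothing in the plan aligns the two. The upward shift is about 4 to 7 points per arm if PFS is exponential, the medians are true progression times and deaths are 0 to 30% of events. It is about 2 to 5 points with 14 to 28 days of scan drift, and about 3 points or less above a smooth curve if the medians are scan-detected. The direction is upward in each of these cases; the size depends on assumptions that the documents do not settle. The log-rank test is little affected and the between-arm difference moves by less than 1 point. This is a cheap improvement, not a flaw in the primary test.

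**What to change.** 1. In Section 7, reconcile footnote 8 with Section 7.1.2 so that scans run on a fixed calendar from a stated anchor (randomization or first dose), regardless of cycle delays. Without this, the second step does not work.
2. In Sections 11.4 and 2.2.1, report PFS at the week-40 assessment, read from the Kaplan-Meier curve after that window has closed, in place of or beside the nine-month figure. Day 294 is day 287 plus 7 days for a start up to 5 business days after randomization.
3. Set data cut-off at least 42 weeks (294 days) after the last randomization.

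The cost is wording and about 3 more weeks (294 − 274 = 20 days) before cut-off. The stated per-arm figures become slightly less favourable. The log-rank comparison stays as planned.

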## 11.5 Analysis Plan for Secondary Objectives

OS will be estimated for each arm using the method of Kaplan and Meier. Median OS will be reported along with a 95% confidence interval. OS will be compared between the two arms using a logrank test. RR will be estimated for each arm and reported along with exact 95% confidence intervals. A Fisher's exact test will be used to compare RR between the two arms. Toxicities will be described for each arm using frequency tables. Fisher's exact tests will be used compare toxicities between arms. The ITT analysis dataset will be used for secondary analyses related to OS and RR. The safety analysis dataset will be used for analyses related to toxicities.

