# **SYNOPSIS**

TITLE	Phase II Randomized, Double-Blind Study of mFOLFIRINOX plus Ramucirumab versus mFOLFIRINOX plus placebo in Advanced Pancreatic Cancer Patients		
SHORT TITLE	Phase II Randomized Trial of mFOLFIRINOX +/- Ramucirumab in Advanced Pancreatic Cancer		
PHASE	II		
OBJECTIVES	Primary Objective: Estimate and compare progression free survival (PFS) of mFOLFIRINOX plus Ramucirumab (RAM) versus mFOLFIRINOX plus placebo in subjects with recurrent or metastatic pancreas cancer (PCA) who present for first line chemotherapy treatment.		
	
 
Secondary Objectives:
 
Estimate and compare the median overall survival (mOS) in each arm.
 
Evaluate and compare the response rate (RR) in each arm.
 
Evaluate and compare the toxicities in each arm.
 
		
STUDY DESIGN	Phase II, multicenter, double-blinded, randomized, 2-arm trial evaluating efficacy and safety of mFOLFIRINOX plus ramucirumab (Arm A) vs. mFOLFIRINOX plus placebo (Arm B) in 85 subjects with advanced PCA, not amenable to curative treatment. Both arms will continue treatment until disease progression or unacceptable toxicity.		
ELIGIBILITY CRITERIA	Each of the criteria in the checklist that follows must be met in order for a subject to be considered eligible for this study.		
	
 
Inclusion Criteria
 
Written informed consent and HIPAA authorization for release of personal health information. NOTE: HIPAA authorization may be included in the informed consent or obtained separately.
 
Age ≥ 18 years at the time of consent.
 
ECOG Performance Status of 0-1 within 7 days prior to registration.
 
Histologic or cytological diagnosis of recurrent or metastatic pancreas adenocarcinoma (PCA) who present for first line chemotherapy treatment.
 
No prior first line systemic treatment (prior adjuvant or neoadjuvant treatment is permitted). Subjects whose disease has progressed after 6 months of last systemic chemotherapy or
 
		

- chemo-radiation in the adjuvant or neoadjuvant setting are eligible.
- 6. Measurable disease determined using guidelines of RECIST 1.1. Baseline tumor assessment should be performed using high resolution CT scans or MRI.
- 7. Urine protein < 1+ on dipstick test or routine urinalysis. If the proteinuria on these tests is  $\ge 2+$ , then a 24-hour urine test must be collected and must demonstrate < 1 g protein in 24 hours to allow participation

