# 6.3 Protocol Therapy Discontinuation

In addition to discontinuation from therapy related to toxicities, a subject will also be discontinued from protocol therapy and followed up per protocol under the following circumstances:

- Evidence of disease progression
- The site physician thinks a change of therapy would be in the best interest of the subject
- The subject requests to discontinue protocol therapy, whether due to unacceptable toxicity or for other reasons
  - o In case a subject decides to prematurely discontinue protocol therapy ("refuses treatment"), the subject should be asked if she or he may still be contacted for further scheduled study assessments. The outcome of that discussion should be documented in both the medical records and in the eCRF.
- A female subject becomes pregnant
- If protocol therapy is interrupted for  $\geq 30$  days.

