## 11.9 Analysis Datasets

The intention-to-treat (ITT) analysis dataset includes all subjects who meet the eligibility criteria and are registered onto the study irrespective of their compliance to the planned course of treatment. The intention-to-treat principle asserts that the effect of a treatment policy can be best assessed by evaluating on the basis of the intention to treat a subject (i.e. the planned treatment regimen) rather than the actual treatment given. It has the consequence that subjects allocated to a treatment group should be followed up, assessed and analyzed as members of that group irrespective of their compliance to the planned course of treatment

The safety analysis dataset includes all subjects who are randomized and receive at least one dose of study treatment (on either arm). Subjects will be analyzed for safety according to the treatment actually received.

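### Section 11.5 compares toxicity between arms as per-subject counts over a window whose length depends on progression, with no common window or exposure summary alongside

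*Combined protocol and SAP*

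**What the plan says.** The analysis plan for the toxicity objective is two sentences in Section 11.5. "Toxicities will be described for each arm using frequency tables", and then "Fisher's exact tests will be used compare toxicities between arms". The same section assigns these analyses to the safety dataset, which Section 11.9 defines by subject: "The safety analysis dataset includes all subjects who are randomized and receive at least one dose of study treatment". That definition sets no limit on the period over which events count.

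The recording period is in Section 10.2.1: from signed consent to 30 days after study drug is discontinued. Treatment has no fixed number of cycles. The Synopsis says "Both arms will continue treatment until disease progression or unacceptable toxicity", and Section 6.3 adds physician decision, subject request, pregnancy and interruption of 30 days or more.

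Section 11.10 gives the design expectation: "The expected progression free survival for mFOLFIRINOX in metastatic pancreatic cancer is 6 months", and adding ramucirumab "would be expected to increase the median PFS to at least 9 months". Fixed toxicity windows exist only in Sections 11.6.1 and 11.6.2 (first four weeks, first cycle), and they serve the stopping rules. Section 11.13 tabulates withdrawals and their reasons. No section plans a treatment-duration summary, an exposure-adjusted rate or a time-to-event analysis of toxicity.

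**The concern.** Fisher's exact test takes one yes or no per subject and ignores how long the subject was at risk. The text does not use the term ever/never, but Fisher's tests on frequency tables imply it. If ramucirumab delays progression, Arm A receives more cycles of the shared mFOLFIRINOX backbone and is observed for longer. Late or cumulative toxicities of that backbone would then be counted in more Arm A subjects even if their monthly risk were the same in both arms. The table cannot separate an added hazard from added time, and the plan supplies nothing beside it that would. What is at stake is how the toxicity objective is read when the PFS effect is the one hoped for.

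**Working it through.** **The plan's own design figure.** With HR = 6/9 = 0.6667, one-sided alpha 0.20 and power 0.80, the Schoenfeld formula gives 4(0.8416 + 0.8416)²/(ln 0.6667)² = 68.9, so 69 events. Exponential PFS with 24 months of uniform accrual and 9 months of follow-up gives 70.3 expected events from 85 subjects. Power is 0.805 by formula and 0.801 by simulation, against 0.8014 stated. Dropout: 85/0.90 = 94.4, so 95. The figures reproduce, so the same inputs are used below.

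**Model.** The documents give no toxicity time course, so these are assumptions.
- Treatment time T equals PFS and is exponential, with λ = ln 2/6 = 0.1155 per month (control) and ln 2/9 = 0.0770 (Arm A).
- The tail is d = 30/30.4375 = 0.986 months (Section 10.2.1).
- Time from entry to the 33-month cut-off, C, is uniform on 9 to 33 months (Section 11.10).
- The observation window is W = min(T + d, C).
- The toxicity hazard h is constant and identical in both arms.

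**Mean window.** E[W] = d + (1 − q)/λ, with q = e^(λd)·[e^(−9λ) − e^(−33λ)]/(24λ).
- Control: q = 0.134, so 0.986 + 0.866/0.1155 = 8.5 months.
- Arm A: q = 0.246, so 0.986 + 0.754/0.0770 = 10.8 months.
- Ratio: 1.27.

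**Incidence.** P(event) = 1 − E[e^(−hW)], where
E[e^(−hW)] = e^(−hd)·λ/(λ+h)·[1 − e^((λ+h)d)·g] + e^(λd)·g and g = [e^(−9(λ+h)) − e^(−33(λ+h))]/[24(λ+h)].

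Example, with h = 0.0697 chosen so that control incidence is 40%:
- Control: g = 0.0420; 0.553 + 0.047 = 0.600, so 40.0%.
- Arm A: g = 0.0736; 0.448 + 0.079 = 0.528, so 47.2%.

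The last column is the chance that Fisher's test declares Arm A more toxic. It is an exact binomial sum for 43 versus 42 subjects. The test is assumed two-sided at 5%, because the plan states no level. With truly equal incidence this chance is about 2%.

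| Control | Arm A, no drug effect | Excess (points) | Fisher false finding against Arm A |
|---|---|---|---|
| 10% | 12.5% | 2.5 | 4.5% |
| 20% | 24.6% | 4.6 | 6.3% |
| 30% | 36.2% | 6.2 | 7.8% |
| 40% | 47.2% | 7.2 | 7.9% |
| 50% | 57.7% | 7.7 | 8.0% |

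**Sensitivity at a 40% control incidence.**
- Onset confined to the first 1, 2 or 4 months: excess 0.0, 0.3 or 1.4 points.
- 25% or 50% of control subjects stopping for reasons other than progression, with the same added stopping hazard in Arm A (0.0385 or 0.1155 per month added to each λ): excess 5.5 or 3.6 points.
- An extra stopping hazard in Arm A alone of 0.1155 − 0.0770 = 0.0385 per month removes the difference. That means one third (0.0385/0.1155) of Arm A stops before progression. Beyond that, the artefact favours Arm A.

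**Early common window.** With the same hazards as in the table but counting only events in cycles 1 to 4 (16 weeks), the excess is 0.1 to 0.9 points. In the 40% row it is 20.4% versus 21.1%.

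**The case against.** The strongest reply is that cumulative incidence over the regimen as given is a legitimate measure of patient burden and conventional in a phase II trial. That stands, and it is why the planned tables should stay.

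The model can also be challenged. Treatment stops for reasons other than progression. Tables 5 to 8 reduce or stop the backbone drugs after toxicity, so a constant hazard is unlikely. Many toxicities appear early. All of this stands and mostly shrinks the artefact, as the sensitivities show. It does not remove it for late or cumulative toxicities.

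Events per patient-month carry a bias of their own. If toxicity is early and equal in both arms, dividing by mean windows of 8.5 and 10.8 months gives a rate ratio of 8.5/10.8 = 0.79, and Arm A looks safer than it is. This stands, so a rate cannot replace the planned comparison. A cycles 1 to 4 window is not perfectly common either: under the design medians about 35% of control and 25% of Arm A progress before week 16. The residual artefact is nevertheless below 1 point at these hazards.

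A reader might infer that Arm A is observed 50% longer. That would need treatment to continue without a data cut. Even then, with the tail, the mean windows are 9.6 versus 14.0 months (ratio 1.45), and the planned cut-off brings the ratio to 1.27. A reader might also infer that starting AE collection at consent favours one arm. It does not: the period before dosing is the same in both randomized, blinded arms. Whether pre-dose events enter the tables is a minor point of definition.

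**Conclusion.** The point holds in a limited form. The Section 11.5 comparison is confounded with time on treatment whenever PFS differs, and nothing planned beside it would show by how much. Under the design's 6 versus 9 months and the stated assumptions, the false excess in Arm A is about 2.5 to 7.7 percentage points for control incidences of 10 to 50%. It is near zero for toxicities confined to the first one or two months, smaller when subjects stop for other reasons, and reversed if Arm A stops sufficiently earlier for toxicity.

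Two stronger readings are tempting and not supported. One is that Arm A will necessarily look more toxic: the direction depends on stopping patterns that the documents do not give. The other is that a go/no-go decision is compromised: no section ties a decision, or even a significance level, to these Fisher's tests. The effect is confined to a secondary objective. The primary PFS test and the four-week stopping rules are untouched. This is a cheap improvement to make before unblinding, not a flaw in the trial's main conclusion.

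**What to change.** In Section 11.5, keep the frequency tables and Fisher's tests as planned and pre-specify alongside them:

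- (a) a between-arm comparison in a common early window, for example worst grade in cycles 1 to 4;
- (b) time to first event or cumulative incidence, with end of treatment for progression or death as a competing event, and/or events per patient-month labelled as assuming a constant hazard. A cumulative incidence curve still carries the exposure difference at later times, but shows when the arms separate;
- (c) treatment duration by arm.

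One sentence saying whether events before first dose are counted would settle the minor definitional point.

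The cost is analysis wording and a few tables. No visits, subjects or clinical rules change. The inputs are AE onset and dosing dates. The protocol has sites record AEs on the eCRF and follow a dosing calendar but does not list the eCRF fields, so the availability of these dates should be confirmed. The downsides are the extra output, and that late cumulative toxicity falls outside the fixed window and must be read from (b) and the planned tables.
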